5. MILESTONES

Milestone	Planned date	Actual Date
Start of data collection	01 July 2020	01 July 2020
End of data collection	01 August 2020	01 August 2020
Final study report	30 June 2021	29 June 2021

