8. RESEARCH METHODS

8.1. Study Design

- **Retrospective analysis** of patients with RA that received etanercept from Baghdad Teaching Hospital (Rheumatology center) from May 2012 until August 2019 (inclusion and exclusion criteria will apply for selecting patients).
- **Primary objective:** Determine the clinical impact of RF and anti-CCP for management (etanercept) in patients with RA compared to negative RF and anti-CCP in RA patients.

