8.2. Setting

Patients and Methods

Data will be collected from the Baghdad Teaching Hospital registry. The rheumatology patient registry is a prospective longitudinal multicenter cohort initiated in 2012. It captures all patients treated with biologic therapies managed in the rheumatology department. The decision to initiate and maintain the treatment is guided by the American College of Rheumatology (ACR) recommendations.

Study population

Patients will be included in the study if they meet the American College of Rheumatology/The European League Against Rheumatism (EULAR) 2010 criteria for Rheumatoid Arthritis,⁵ with at least 1 year of follow-up after starting their first biologic therapy. This includes patients who were in monotherapy or in combo-therapy with concomitant conventional DMARDs.

Hypothesis

Our hypothesis is that there is no difference in response between seropositive and seronegative RA patients to Enbrel.

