8.3. Data Sources

Patients will be identified from the rheumatology patient registry with rheumatoid arthritis and obtained information on patient demographics (age, gender), education level (years), present smoking status, disease duration (years), current MTX and steroid therapy (yes/no), baseline Disease Activity Score 28(DAS28) and Clinical Disease Activity Index (CDAI), RF status, anti-CCP status. Primary Outcomes: DAS28 and CDAI in last follow-up visit.

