8.6. Data Analysis

Categorical covariates will be described by frequency distribution while continuous covariates will be expressed in terms of their mean and standard deviation or median and interquartile range as appropriate. Patients will be divided for seropositive RA and seronegative RA (according to anti-CCP status). The unadjusted comparisons between groups of the covariates and the outcomes will be evaluated using chi² tests for categorical data, while for continuous data, the Student's t-test will be used for normally distributed variables and the Kruskall-Wallis test for non-parametric data.

The effect of biologic treatment response in patients with sero-positive RA will be determined with a multivariate analysis by using a stepwise linear regression model. The response variable is defined as DAS28 and CDAI at last visit. The baseline variables considered demographic data, disease duration (years), methotrexate (yes/no), current steroid therapy (yes/no), baseline DAS28 and CDAI, RF positive (yes/no), anti-CCP (yes/no), and present smoking (yes/no).

The effect of response will be determined by using change from baseline in DAS28 and CDAI at the last visit. A p-value of <0.05 is considered statistically significant, without multiplicity adjustment, for this post-hoc analysis.

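### RF and anti-CCP, the exposures of the primary objective, are only candidates in a stepwise regression, so either can end without an adjusted estimate or with one reported only because it was selected

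*Combined protocol and SAP*

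**What the plan says.** All references are to the combined protocol and SAP.

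- **Objective (Section 8.1):** "Determine the clinical impact of RF and anti-CCP for management (etanercept) in patients with RA", compared with patients negative for these markers. Both markers are named in advance.
- **Hypothesis (Section 8.2):** "there is no difference in response between seropositive and seronegative RA patients to Enbrel". No margin is given.
- **Adjusted analysis (Section 8.6):** the effect "will be determined with a multivariate analysis by using a stepwise linear regression model". The candidates are demographics, disease duration, methotrexate and steroid use, then "baseline DAS28 and CDAI, RF positive (yes/no), anti-CCP (yes/no), and present smoking (yes/no". There are no entry or removal thresholds, no forced terms, no fixed adjusted model, and no rule for reporting a marker that is not selected.
- **Unadjusted analysis (Section 8.6):** "Patients will be divided for seropositive RA and seronegative RA (according to anti-CCP status". RF does not define a comparison group.
- **Outcome:** Section 8.3 has "Primary Outcomes: DAS28 and CDAI in last follow-up visit", and Section 8.6 uses the same response variable for the regression. Section 8.6 then adds: "The effect of response will be determined by using change from baseline in DAS28 and CDAI at the last visit".
- **Study size (Section 8.4):** none is set; all eligible patients enter.

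**The concern.** Stepwise selection lets a p-value rule decide which terms stay. That may be tolerable for nuisance covariates, but here the rule also acts on the two variables the study exists to evaluate. Three consequences follow from the text alone.

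1. If anti-CCP is not selected, only its unadjusted comparison remains.
2. If RF is not selected, nothing remains, because the stepwise model is the only place where RF is related to outcome.
3. If one marker is selected and the other is not, the reported coefficient is conditional on passing the entry test and also absorbs part of the omitted, correlated marker's effect.

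The hypothesis of no difference makes this worse. If it is true, both markers will usually be deleted. Deletion can then be read as confirmation, although no adjusted interval shows which differences the data exclude.

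The outcome wording adds a smaller problem. Last-visit value and change from baseline give the same serostatus coefficient only if the baseline of the same index is in the model, and stepwise selection does not guarantee that.

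**Working it through.** The plan states no sample size, power, SD or effect, so there is no figure of its own to reproduce. The structural point needs no numbers; what follows only sizes it.

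**Inputs from the documents.** RF positive 70% and anti-CCP positive 65% (study information table; Section 6 gives 65% to 80% for anti-CCP). Ten candidates from Section 8.6, taking demographics as age and sex.

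**Assumed inputs.** Residual SD 1.2 DAS28, baseline slope 0.3, baseline DAS28/CDAI correlation 0.8, RF/anti-CCP correlation φ = 0.48, entry p < 0.05, removal p > 0.10, N = 100 to 800.

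**Step 1: what a fixed model would deliver.** Approximate standard error for anti-CCP:

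SE = 1.2 / √(N × 0.65 × 0.35 × (1 − 0.48²)) = 1.2 / √(0.175 N) = 0.287/0.203/0.143/0.101 at N = 100/200/400/800.

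The 95% half-width is 1.96 × SE = 0.56/0.40/0.28/0.20. Simulation with all covariates gives 0.60/0.41/0.29/0.20.

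**Step 2: what a selected marker reports.** If RF is left out, the anti-CCP coefficient absorbs β_RF times the slope of RF on anti-CCP. That slope is 0.48 × √(0.70 × 0.30 / (0.65 × 0.35)) = 0.46. With both true effects 0.3, the anti-CCP coefficient centres on 0.3 + 0.3 × 0.46 = 0.44 before any selection effect. To enter without RF, it must exceed about 1.96 × 1.2 / √(0.2275 N) = 0.49/0.35/0.25/0.17. At N = 100 and N = 200, a positive estimate that enters this way therefore exceeds the true 0.3.

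**Step 3: simulation of stepwise against a fixed model** (4,000 runs per cell; 3,000 for the RF row and the φ range).

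| Result | N=100 | 200 | 400 | 800 |
|---|---|---|---|---|
| *Anti-CCP 0.3, RF 0* | | | | |
| Anti-CCP dropped | 79% | 65% | 38% | 10% |
| Fixed model not significant | 83% | 70% | 46% | 16% |
| Mean estimate when kept | 0.67 | 0.49 | 0.38 | 0.32 |
| When dropped, fixed-model 95% CI still includes 0.6 | 79% | 52% | 6% | 0% |
| Baseline DAS28 not selected | 39% | 15% | 4% | 0.3% |
| *Anti-CCP 0.6, RF 0* | | | | |
| Anti-CCP dropped | 41% | 12% | 1% | 0% |
| Mean estimate when kept | 0.77 | 0.64 | 0.60 | 0.60 |
| *Both 0.3* | | | | |
| Exactly one marker kept | 52% | 78% | 77% | 36% |
| Anti-CCP only | 27% | 39% | 40% | 20% |
| RF only | 25% | 39% | 37% | 16% |
| RF dropped (separate runs) | 74% | 58% | 43% | 18% |
| Anti-CCP mean when kept | 0.70 | 0.55 | 0.44 | 0.35 |
| Its 95% CI coverage when kept | 73% | 81% | 85% | 91% |

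In the last scenario the fixed model averages 0.30 with about 95% coverage at every N. At N = 400, coverage when kept runs from 92% (φ = 0.29) to 62% (φ = 0.67). With no true effect, anti-CCP is kept in 4% to 6% of runs, and neither marker in about 90%.

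A separate simulation (residual SD 1, eleven candidates, both effects 0.2 SD, 500 runs) shows the same pattern: neither marker kept in 60%/37%/11% at N = 100/200/400, and mean anti-CCP when kept 0.58/0.42/0.33.

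**Step 4: value versus change.** Let Y be the last-visit score and B its baseline. Regressing Y − B instead of Y on B and the other terms lowers the coefficient of B by 1 and changes no other coefficient. A simulated data set confirms this: anti-CCP 0.472, SE 0.211 for both. Without adjustment, the difference in Y minus the difference in Y − B equals the baseline gap between groups.

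**The case against.** - **An anti-CCP comparison is always made.** True: the unadjusted one is planned whatever the model selects. For anti-CCP the loss is the adjusted estimate; only RF can be left with nothing.
- **The sizes rest on assumptions.** This stands. Residual SD and baseline slope were not varied, anti-CCP prevalence was held at 65%, and CDAI was not simulated as an outcome. Drop rates largely mirror low power, false retention is near nominal, and bias fades when one effect is large. With a single true effect of 0.3, coverage when kept was 83% at N = 100 but about 95% to 96% at N = 400 and 800. However, Section 8.4 sets no sample size, so the plan cannot rely on a large one, and the reporting gap exists at any N.
- **No passage says non-selection will be taken as proof of no difference.** Correct: that is a risk, not a planned step.
- **The regression might be meant for seropositive patients only.** Section 8.6 is loosely worded here. But anti-CCP yes/no is a candidate, and it would be constant in a group defined by anti-CCP positivity. That reading does not fit, though the population should be stated.
- **The analysis is called post hoc and is finished.** Section 5 dates the "Final study report" 29 June 2021, so prespecification cannot be restored. The post-hoc label is used to justify no multiplicity adjustment; it does not supply a missing estimate.

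**Conclusion.** The concern holds and must be fixed. Followed exactly, the plan can leave RF with no estimate and anti-CCP with no adjusted one, so the primary analysis can fail to answer the primary objective. This conclusion rests on the text alone.

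The size is illustrative. Under the stated assumptions, with two modest correlated effects, selection usually reports one marker only for N of 100 to 400 and overstates it: 0.70 against 0.30 at N = 100, and 0.44 at N = 400. The distortion is small at N = 800, or when one effect is large and N is at least moderate. The harm is a missing or selectively reported estimate, not lost power. The value-versus-change ambiguity is secondary and disappears once the same-index baseline is always in the model.

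**What to change.** Replace stepwise selection in Section 8.6 with one fixed-term linear model per index, fitted in all eligible patients, with last-visit DAS28 or CDAI as outcome. Always include anti-CCP, RF, the baseline of the same index, age, sex, disease duration, methotrexate, steroid use and smoking. The other index's baseline may be left out. Report both serostatus coefficients with 95% intervals whatever their p-values, and draw no conclusion of no difference from non-selection or non-significance. Any stepwise model should be labelled exploratory.

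State that change from baseline is descriptive or is analysed with the same baseline term, and that the unadjusted comparisons are not used to judge response.

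The cost is amended text, a re-run labelled as done after the final report, and a report update. All variables are already listed in Sections 8.3 and 8.6, and no new data or software is needed. A few degrees of freedom are spent, and wide intervals become visible: about ±0.60 DAS28 at N = 100 and ±0.29 at N = 400 under the assumptions above.

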8.4. Study Size

There is no pre-identified study size sample. All patients that meet the criteria will be entered into the study.

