8.8. Limitations of the Research Methods

Missing data that could lead to bias is an identified limitation of this study.

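### Read with section 8.3, education level is the only extracted baseline item not named in the section 8.6 regression list, and no reason is given

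*Combined protocol and SAP*

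**What the plan says.** Section 8.3 lists what is taken from the registry. It begins "patient demographics (age, gender), education level (years), present smoking status, disease duration (years" and continues "current MTX and steroid therapy (yes/no), baseline Disease Activity Score 28(DAS28) and Clinical Disease Activity Index (CDAI), RF status, anti-CCP status". Education has its own place and unit, outside the parenthesis that explains demographics.

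Section 8.6 gives the inputs to the regression: "The baseline variables considered demographic data, disease duration (years), methotrexate (yes/no), current steroid therapy (yes/no), baseline DAS28 and CDAI", then "RF positive (yes/no), anti-CCP (yes/no), and present smoking (yes/no". Education is not named, and demographic data is not defined there. The method is a "multivariate analysis by using a stepwise linear regression model", with DAS28 and CDAI at the last visit as responses.

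Section 8.8 adds: "Missing data that could lead to bias is an identified limitation of this study". The protocol does not say how complete the education field is.

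**The concern.** Serostatus is not randomised. Section 8.6 describes its direct group comparisons as unadjusted, so the regression is the only place where differences between seropositive and seronegative patients can be taken into account. Education is also the only socioeconomic variable extracted. If it is related to both serostatus and last-visit disease activity, given the other covariates, omitting it leaves some bias in the RF and anti-CCP estimates. If it is related to outcome alone, omitting it leaves residual variance that could have been removed.

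There is also a reproducibility problem. One analyst working from section 8.6 could treat demographic data as age and gender, and another could include education. They would fit different models from the same text.

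**Working it through.** The plan states no sample size ("There is no pre-identified study size sample"), effect size or standard deviation, so there is no figure to reproduce. The check is a comparison of the two lists, followed by illustrative arithmetic on assumed inputs.

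**1. The lists side by side**

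| Extracted (8.3) | Named in regression (8.6) |
|---|---|
| Age, gender | Yes, as demographic data |
| Education level (years) | Not named |
| Present smoking | Yes |
| Disease duration | Yes |
| Methotrexate, steroid | Yes, both |
| Baseline DAS28, CDAI | Yes, both |
| RF, anti-CCP | Yes, both |

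There are 11 items, 10 matched and one unmatched. If demographic data were read broadly enough to cover education, none would be unmatched.

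**2. Possible bias from omission (assumed inputs)**

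Bias = effect of education on last-visit DAS28 × difference in education between serogroups, both conditional on the other covariates.

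- Per year: 0 to 0.05 DAS28 units × 0 to 2 years = 0 to 0.10 units.
- Per SD: 0.1 to 0.3 units × 0.1 to 0.3 SD = 0.01 to 0.09 units.

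The second range starts above zero only because both of its inputs do. If either link is absent, the bias is zero. The documents offer no basis for a corresponding CDAI figure.

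**3. Possible precision gain against loss of cases (assumed inputs)**

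- Gain in SE if education explains a share R² of the residual variance: 1 − √(1 − R²). For R² = 0.01 this is 0.5%; for R² = 0.05 it is 2.5%.
- Inflation of SE if a share m of records lacks education and is dropped: 1/√(1 − m) − 1. For m = 0.05 this is 2.6%; for m = 0.30 it is 19.5%.
- Net SE ratio: √(1 − R²)/√(1 − m). It equals 1 when m = R², so 5% missing cancels the 2.5% gain and 1% missing cancels the 0.5% gain.

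**4. What listing education under stepwise selection would achieve**

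Assume entry at two-sided 0.05 (the plan gives 0.05 as its significance level but states no entry rule), an education SD of 4 years, a residual DAS28 SD of 1.2 and an effect of 0.02 to 0.05 units per year. With λ = effect × 4 × √N / 1.2, the probability of entry is Φ(λ − 1.96) + Φ(−λ − 1.96).

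| N | Effect 0.02 | Effect 0.05 |
|---|---|---|
| 100 | 0.10 | 0.38 |
| 200 | 0.16 | 0.65 |
| 400 | 0.27 | 0.92 |

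Merely adding the variable to the candidate list would therefore often leave it out of the final model.

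**The case against.** The strongest objection is that no omission is established. Education in years is often grouped with demographics, and section 8.6 does not define the term. That reading is possible but is the weaker one. The protocol's only gloss limits demographics to age and gender, and section 8.6 names every other separately listed item. The ambiguity would need the same edit in any case.

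A reader might infer that education is a confounder. The documents do not support this: they relate education neither to serostatus nor to response. Smoking, disease duration and the baseline activity scores are already candidates and may cover part of any such path. This part of the objection stands.

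A reader might also infer that the adjustment costs nothing because education is recorded for every patient. Section 8.3 plans the extraction but says nothing about completeness, and section 8.8 names missing data as a limitation. The break-even above shows that a small share of missing records would cancel the gain in precision.

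Finally, stepwise selection is the larger threat to adjustment. Forcing education in alone, while baseline DAS28, smoking or even anti-CCP could still be dropped, would make little sense. That also stands, and it determines the form of the fix.

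**Conclusion.** On the protocol's own wording, education level is extracted but not named in the only adjusted analysis, and no reason is given. The finding rests on reading demographic data in section 8.6 as section 8.3 explains it.

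The consequence is probably small: about 0 to 0.1 DAS28 units in the serostatus difference, and possibly none. Any gain in SE is about 0.5% to 2.5%, before allowing for lost cases. All these sizes rest on assumed inputs. The documents do not determine the direction of any bias, nor whether a conclusion would change. This is a worthwhile clarification and a modest improvement, not a flaw that undermines the study.

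**What to change.** - In section 8.6, define demographic data as age and gender, and name education level (years) as a covariate in both the DAS28 and the CDAI model.
- Enter education together with the other listed baseline covariates as a pre-specified adjustment set, in place of stepwise selection.
- Report how many records lack education. If the loss of cases is material, show the serostatus estimate with and without it.

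The cost is a short edit to section 8.6, one degree of freedom per model for education, and possible complete-case loss. Section 5 gives 29 June 2021 as the actual date of the final report, and this protocol version is dated 27 July 2021. The result should therefore be presented as a labelled supplementary analysis. It needs no data beyond what section 8.3 already plans to extract.

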NON-INTERVENTIONAL (NI) STUDY PROTOCOL

Study Information

Title	The impact of RF, and anti-CCP on RA patients in response to Etanercept
Protocol number	B1801417
Protocol version identifier	3.0
Date	27 July 2021
Active substance	etanercept
Medicinal product	etanercept
Research question and objectives	The RF and anti-CCP are found to be positive in 70% and 65% of RA patients respectively. Researchers have found that RF and anti-CCP have an impact on RA response. The objective is to evaluate the impact of RF and ACCP on RA patients in response to Enbrel from the local data.
Author	PPD [REDACTED] – MD, M.Sc. PPD [REDACTED] Pfizer Inc. - Iraq
This document contains confidential information belonging to Pfizer. Except as otherwise agreed to in writing, by accepting or reviewing this document, you agree to hold this information in confidence and not copy or disclose it to others (except where required by applicable law) or use it for unauthorized purposes. In the event of any actual or suspected breach of this obligation, Pfizer must be promptly notified.	

PFIZER CONFIDENTIAL

[figure not shown]
[REDACTED]

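### The plan has no adjusted estimate of the primary contrast (RF and anti-CCP positive versus negative), and stepwise selection will usually keep one marker and drop the other, partly by chance

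*Combined protocol and SAP*

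**What the plan says.** Section 8.1 sets the main aim of the study: "Determine the clinical impact of RF and anti-CCP for management (etanercept) in patients with RA compared to negative RF and anti-CCP in RA patients". The hypothesis in section 8.2 is that "there is no difference in response between seropositive and seronegative RA patients to Enbrel".

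Section 8.6 offers two routes to an answer:

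- **Unadjusted.** "Patients will be divided for seropositive RA and seronegative RA (according to anti-CCP status"). RF plays no part in this split.
- **Adjusted.** The effect is to be determined "with a multivariate analysis by using a stepwise linear regression model", for DAS28 and CDAI at the last visit. The candidate list includes "RF positive (yes/no), anti-CCP (yes/no), and present smoking (yes/no"), along with demographics, disease duration, methotrexate, steroids and baseline disease activity.

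On significance, section 8.6 says: "A p-value of <0.05 is considered statistically significant, without multiplicity adjustment". It does not give the direction of the stepwise procedure or its entry and removal thresholds, and it forces neither marker into the model. It plans no combined serostatus variable, sum of coefficients, joint test or interaction. It has no rule for patients whose two results disagree. Section 8.4 sets no sample size.

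**The concern.** The objective is about the two markers together, while the adjusted model treats them as two competing candidates. Whatever the selection retains, no reported coefficient is the double-positive versus double-negative difference:

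- **Both kept:** each coefficient is the effect of one marker at a fixed status of the other. Under additivity the objective's contrast is their sum, which is neither reported nor tested.
- **One kept:** its coefficient compares two groups that each contain discordant patients.
- **Neither kept:** there is no estimate.

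RF and anti-CCP overlap, so once one is in the model the other adds little and tends to stay out. The study could then report that one antibody predicts response to etanercept and the other does not, when both contribute equally and sampling variation decided which was kept. For a study meant to describe the impact of both markers, that would be a misleading result.

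**Working it through.** The plan states no power, effect or sample size, so it has no figure to reproduce. The calculation below shows size and direction under stated assumptions.

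**Inputs from the documents.** RF positive 70% and anti-CCP positive 65% (study information table: "The RF and anti-CCP are found to be positive in 70% and 65% of RA patients respectively"); significance at 0.05, taken as two-sided.

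**Assumptions.** n = 200; residual DAS28 SD 1.2; true double-positive versus double-negative difference 0.6, made up of 0.3 from each marker; correlation φ between markers 0.4, 0.6 or 0.7; stepwise entry at p<0.05; no other covariates.

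**Overlap at φ = 0.6.** The marker variances are 0.70×0.30 = 0.21 and 0.65×0.35 = 0.2275, and √(0.21×0.2275) = 0.2186. P(double positive) = 0.70×0.65 + 0.6×0.2186 = 0.586. Discordant share = 0.70 + 0.65 − 2×0.586 = 0.178. Over φ = 0.4 to 0.7 the discordant share falls from 27% to 13%.

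**One marker kept.** With anti-CCP alone in the model, its coefficient targets β_CCP + β_RF × φ√(0.21/0.2275) = 0.3×(1 + 0.961φ). This gives 0.42, 0.47 and 0.50 at φ = 0.4, 0.6 and 0.7. The objective's contrast is 0.60.

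**Both markers kept, φ = 0.6.**

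- SE(RF) = √[1.2²/(200×0.21×(1−0.36))] = √(1.44/26.88) = 0.231
- SE(anti-CCP) = √(1.44/29.12) = 0.222
- Covariance = −(1.44/200)×0.6/(0.2186×0.64) = −0.0309
- SE(sum) = √(0.0536 + 0.0495 − 2×0.0309) = 0.203

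The ratios of effect to SE are 0.3/0.231 = 1.30, 0.3/0.222 = 1.35 and 0.6/0.203 = 2.96, so power is about 25%, 27% and 84%.

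**What the stepwise rule reports** (simulation, n = 200, equal split; percentages are rounded):

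| | φ = 0.4 | φ = 0.6 | φ = 0.7 |
|---|---|---|---|
| Exactly one marker kept | 74% | 85% | 88% |
| Both kept | 6% | 2% | 1% |
| Neither kept | 20% | 14% | 12% |
| Combined contrast not significant | 23% | 17% | 15% |
| Both forced in, neither coefficient significant | 42% | 49% | 58% |

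At φ = 0.6, RF alone and anti-CCP alone are each kept in a little over 40% of runs, so the choice is close to a coin toss.

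**Other settings.** With N = 300, a 0.4 SD effect and φ = 0.4, 0.6 and 0.8, exactly one marker is kept in 75%, 83% and 89% of runs and neither in 20%, 16% and 11%. At N = 600 neither is kept in only 3%, 2% and 1%. At that size and φ = 0.4 both are kept in about 25%, so the share with both kept rises when the sample is large and the overlap modest. Even then the sum is not a planned output.

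**The case against.** **The stronger reading.** A reader might infer that, because both markers sit in one regression, a real seropositivity effect will come out as neither marker mattering. The documents do not support this. The model is stepwise and the markers are only candidates, so a coefficient is conditional on the other marker only when both are retained, which is rare in most settings tried. In the table the stepwise rule keeps neither marker about as often as the combined contrast itself misses. The 'neither' result becomes common only if both markers are forced in and their p-values are read singly.

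**Other points against.**

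- The unadjusted anti-CCP comparison leaves RF out and would often detect a difference. Under the same assumptions its power is 64%, 75% and 80% at φ = 0.4, 0.6 and 0.7, against 79%, 84% and 86% for the combined contrast. This stands, but that comparison is unadjusted and classes patients by anti-CCP only.
- The equal split favours the concern. If one marker carries the whole 0.6, the power of its own coefficient in the two-marker model at φ = 0.6 is 74% (RF) or 77% (anti-CCP), against 84% for the sum. At φ = 0.4 it is 84% or 87%, better than the sum's 79%. A model that keeps only that marker then targets 0.6 + 0 = 0.6, which equals the contrast. This stands and limits the size of the problem.
- The objective can be read as asking about each marker separately, since it does not say how discordant patients are classed. That is a fair reading of loose wording. However, section 8.1 states a comparison with patients negative for RF and anti-CCP, and no planned adjusted result supplies it.

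**Conclusion.** The point holds in this form. The primary objective has no adjusted estimate or test, and this follows from the text of sections 8.1 and 8.6 alone. The likely consequence is a report that one marker matters and the other does not, with the retained marker chosen partly by chance and its coefficient short of the contrast (about 0.42 to 0.50 against 0.60 in the worked case for anti-CCP alone).

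The percentages rest on an assumed sample size, SD, effect, marker correlation and equal split, none of which the documents give. They show direction and rough size and do not predict this dataset. A claim that the plan will usually find neither marker important should not be made.

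**What to change.** In section 8.6:

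1. Exempt RF and anti-CCP from stepwise selection and keep both in one model per outcome (DAS28, CDAI). State that this overrides selection for these two terms.
2. Name the adjusted double-positive versus double-negative difference, with its 95% CI, as the adjusted answer to the primary objective. Take it either as β_RF + β_anti-CCP, stating that this assumes additive effects, or from a serostatus factor (double positive, discordant, double negative), which does not need the double-positive effect to be the sum of two separate ones.
3. Report a 2-df joint test of the two markers.
4. State that a single coefficient is read only as the added contribution of one marker given the other, and that a non-significant one does not show that the marker or seropositivity has no impact.

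Steps 2 to 4 have to accompany step 1, because forcing both markers in and reading them singly is what makes the 'neither' result common.

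The cost is a few sentences and one extra contrast per outcome in the existing software, with no new data. Section 5 shows data collection as complete and the final report as issued, so in practice this is a re-analysis of the existing dataset, to be labelled as such. The downside is that both marker terms stay in each model whatever their p-values, and one more result is reported per outcome.

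### Response is the last-visit score in 8.3 and in one paragraph of 8.6 but change from baseline in the next, and the unadjusted serostatus comparison can change sign between the two

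*Combined protocol and SAP*

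**What the plan says.** Section 8.3 (Data Sources) lists "Primary Outcomes: DAS28 and CDAI in last follow-up visit". In Section 8.6 (Data Analysis), the paragraph on the regression agrees: "The response variable is defined as DAS28 and CDAI at last visit". The next paragraph of 8.6 uses a different quantity: "The effect of response will be determined by using change from baseline in DAS28 and CDAI at the last visit". No text ranks or links the two. The amendment log records only milestone and spelling changes.

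Two analyses could carry either definition.

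- **Group tests.** 8.6 states "Patients will be divided for seropositive RA and seronegative RA (according to anti-CCP status"), and then "The unadjusted comparisons between groups of the covariates and the outcomes will be evaluated using chi² tests for categorical data", with a t-test or rank test for continuous data. These tests contain no baseline term.
- **Regression.** The effect "will be determined with a multivariate analysis by using a stepwise linear regression model". Baseline scores appear only in the list of variables considered: "baseline DAS28 and CDAI, RF positive (yes/no), anti-CCP (yes/no), and present smoking (yes/no"). Both baseline indices are offered, and no term is stated as always included.

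The hypothesis in 8.2 is that response does not differ between seropositive and seronegative patients, so the meaning of response decides what is being tested.

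**The concern.** Serostatus is not randomised, so the two groups may start etanercept at different disease activity. If they do, a raw comparison of last-visit scores carries part of that starting gap forward, while a raw comparison of change tends to reward the group that started higher, because high scores have further to fall. The same patients can then support opposite statements about seropositive disease.

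The plan applies a 0.05 threshold without multiplicity adjustment to data that already exist. With both definitions open, a reader of the results could not tell whether the reported one was chosen before or after the results were seen.

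**Working it through.** The plan states no sample size, effect size, SD or baseline gap, so it has no figure of its own to reproduce. All numerical inputs below are assumptions.

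**Algebra.** Let last = a + b × baseline + g × serostatus, and let D be the baseline mean in seropositive minus seronegative patients.

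- Unadjusted difference in last-visit score: bD + g.
- Unadjusted difference in change: (b − 1)D + g.
- The first minus the second is D, whatever b and g are.
- For D > 0 the signs are opposite whenever −bD < g < (1 − b)D. With g = 0 and 0 < b < 1 they are always opposite in expectation.
- With the same index's baseline in the model and the same other covariates, both outcomes give g with the same standard error and p-value. In simulation the two agreed to within 1e-13.

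Example in DAS28 units, with D = 0.5, b = 0.4, g = 0: last visit 0.4 × 0.5 = +0.20 (seropositive looks worse); change −0.6 × 0.5 = −0.30 (seropositive looks better). Over D = 0.3, 0.5, 0.8, b = 0.2, 0.4, 0.6 and g = −0.2, 0, +0.2, signs were opposite in 18 of 27 combinations, including all 9 with g = 0.

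**False-positive rates of the unadjusted tests.** Assumptions: g = 0, 70% seropositive, two-sided 0.05, unit SD within group at both times (so b equals the correlation r), r = 0.3 or 0.5, n = 150 or 300. The SD of change is √(2(1 − r)), which is 1.183 at r = 0.3 and 1.000 at r = 0.5. The standard error per unit SD is √(1/(0.7n) + 1/(0.3n)), which is 0.178 at n = 150 and 0.126 at n = 300. Non-central t calculation at D = 0.5 SD:

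| n | r | Last-visit difference | Rejects | Change difference | Rejects |
|---|---|---|---|---|---|
| 150 | 0.3 | +0.15 | 13% | −0.35 | 38% |
| 150 | 0.5 | +0.25 | 29% | −0.25 | 29% |
| 300 | 0.3 | +0.15 | 22% | −0.35 | 65% |
| 300 | 0.5 | +0.25 | 51% | −0.25 | 51% |

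Simulation gives 14–51% (last visit) and 29–65% (change), the same within simulation error. With D = 0.2 SD the rates are about 6–15% across both tests; with D = 0 they are 5%. At D = 0.5 SD the two estimates had opposite signs in 76–95% of simulated data sets, but both were significant in opposite directions in only 1–3% (n = 150) and 7–17% (n = 300).

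**The stepwise regression.** With r of 0.3 to 0.5, baseline was non-significant in a regression of last-visit score on baseline in at most 4% of runs at n = 150 and at most 0.05% at n = 300. When stepwise selection itself was simulated with the 0.5 SD gap and no serostatus effect, serostatus was selected in only 3–7% of runs, and the other index's baseline was the only one kept in 0–19%. Frequent loss of baseline needs a weaker association and a smaller sample: at n = 100 with b of 0.1 to 0.2 it was non-significant in 55–87% of runs.

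**The case against.** The strongest reply is that the inference is meant to come from the regression, where baseline is offered and would usually be kept. That stands: the inflated error rates belong to the tests that the plan itself calls unadjusted, and a reader should not carry them over to the regression.

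Second, a reader might infer from Section 6 that seropositive patients must start with higher scores. The text does not say so. It reports a more severe disease course with RF and more active disease during follow-up with anti-CCP. Every patient here is starting a first biologic, which may bring the groups closer at baseline. The 0.5 SD gap is an assumption, and with no gap the two definitions agree.

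Third, one might conclude that baseline adjustment removes all bias. It does so above only because the data were generated from that model. If instead both groups have the same mean change and a 0.5 SD gap persists, the adjusted difference is (1 − r) × 0.5, that is +0.25 to +0.35 SD, and it rejects in 35–82% of runs, while the change comparison stays near 5%. In non-randomised groups, choosing between the two is a choice of estimand.

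Fourth, the plan does not name two primary outcomes: 8.3 gives that label only to the last-visit scores. That is fair, but 8.6 still says the effect of response is determined by change, so the label does not settle which result answers the question.

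**Conclusion.** The conflict is in the current text and should be fixed. The plan gives two meanings of response and does not say which one answers the serostatus question. In the unadjusted tests they differ by exactly the baseline gap and can point in opposite directions. How much this matters depends on a gap that the documents do not report: nothing at zero, modest at 0.2 SD, serious at 0.5 SD. The error rates rest on the assumed correlation of 0.3 to 0.5, 70% seropositive, 150 to 300 patients and no serostatus effect given baseline.

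The documents do not support the stronger readings that the regression itself is badly inflated, or that both definitions would often be significant in opposite directions. The regression's weakness is that nothing secures the same-index baseline or serostatus in the model. That, with the unranked definitions, makes this a point to correct but not one that invalidates the plan.

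**What to change.** In 8.3 and 8.6:

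- Name the last-visit score as the single primary response for each index.
- Analyse it by linear regression with serostatus and the baseline of that same index always in the model: baseline DAS28 for DAS28, baseline CDAI for CDAI. Limit any variable selection to the other covariates.
- Report the adjusted serostatus difference with a 95% CI as the effect on response.
- Present unadjusted last-visit scores and raw change by serostatus as descriptive only.
- State that the estimate is a difference conditional on baseline, which in non-randomised groups need not equal the difference in mean change.

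No new data are needed, because 8.3 already collects both baseline scores. The cost is wording in two sections. Section 5 gives an actual final-report date of 29 June 2021, before this version of 27 July 2021, so the change may also mean a small reanalysis of existing data and a statement in the report of which definition is primary.
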